5.5 Criteria for Taking a Participant Off Protocol Therapy

Duration of therapy will depend on individual response, evidence of disease progression and tolerance. In the absence of treatment delays due to adverse event(s), treatment may continue for until one of the following criteria applies:

- Disease progression
- Intercurrent illness that prevents further administration of treatment
- Unacceptable adverse event(s)
- Participant demonstrates an inability or unwillingness to comply with the oral medication regimen and/or documentation requirements

- Participant decides to withdraw from the protocol therapy
- General or specific changes in the participant's condition render the participant unacceptable for further treatment in the judgment of the treating investigator

Participants will be removed from the protocol therapy when any of these criteria apply. The reason for removal from protocol therapy, and the date the participant was removed, must be documented in the case report form (CRF). Alternative care options will be discussed with the participant.

A Office of Data Quality (ODQ) Treatment Ended/Off Study Form will be filled out when a participant is removed from protocol therapy. This form can be found on the ODQ website or obtained from the ODQ registration staff.

In the event of unusual or life-threatening complications, treating investigators must immediately notify the Overall PI, [name] at [contact].

5.6 Duration of Follow Up

Patients will have a followup visit 30 days from the last dose +/- 7 days or coincide with the date of discontinuation (+/- 7 days) if date of discontinuation is greater than 37 days after last dose. Follow-up visit 2 will be 8-10 weeks (+/- 7 days) from follow-up visit 1. After 2 followup visits, patients will be followed with a phone call every 10-12 weeks for survival information for 2 years after removal from protocol therapy or until death, whichever occurs first. Participants removed from protocol therapy for unacceptable adverse event(s) will be followed until resolution or stabilization of the adverse event.

5.7 Criteria for Taking a Participant Off Study

Participants will be removed from study when any of the following criteria apply:

- Lost to follow-up
- Withdrawal of consent for data submission
- Death

The reason for taking a participant off study, and the date the participant was removed, must be documented in the case report form (CRF).

An ODQ Treatment Ended/Off Study Form will be filled out when a participant comes off study. This form can be found on the ODQ website or obtained from the ODQ registration staff.

6. DOSING DELAYS/DOSE MODIFICATIONS

The descriptions and grading scales found in the revised NCI Common Terminology Criteria for

Adverse Events (CTCAE) version 4.0 will be utilized for dose delays and dose modifications. A copy of the CTCAE version 4.0 can be downloaded from the CTEP website http://ctep.cancer.gov/protocolDevelopment/electronic_applications/ctc.htm.

There will be no dose modifications permitted. Dose reductions or dose escalations are not permitted.

Management Algorithms for Immuno-Oncology Agents

Immuno-oncology (I-O) agents are associated with adverse events that can differ in severity and duration than adverse events caused by other therapeutic classes. Nivolumab and ipilimumab are considered immuno-oncology agents in this protocol. Management algorithms have been developed to assist investigators in assessing and managing the following groups of adverse events: Gastrointestinal, Renal, Pulmonary, Hepatic, Endocrinopathies, Skin, and Neurological.

Early recognition and intervention are recommended according to the management algorithms; and in addition include ophthalmologic evaluations for any visual symptoms in order to evaluate for nivolumab or ipilimumab related uveitis.

The recommendations are to follow the algorithms in the nivolumab investigator brochure for immune related events; while the ipilimumab investigator brochure contains similar algorithms, the algorithms in the nivolumab brochure have been aligned to accommodate combinations as well as nivolumab monotherapy.

For subjects expected who require more than 4 weeks of corticosteroids or other immunosuppressants to manage an adverse event, consider the following recommendations

- Antimicrobial/antifungal prophylaxis per institutional guidelines to prevent opportunistic infections such as *Pneumocystis jiroveci* and fungal infections.
- Early consultation with an infectious disease specialist should be considered. Depending on the presentation, consultation with a pulmonologist for bronchoscopy or a gastroenterologist for endoscopy may also be appropriate.
- In patients who develop recurrent adverse events in the setting of ongoing or prior immunosuppressant use, an opportunistic infection should be considered in the differential diagnosis.

Additional details on the safety of nivolumab and ipilimumab , including results from clinical studies, are available in the IB.

Dose Delay Criteria

Because of the potential for clinically meaningful nivolumab-related AEs requiring early recognition and prompt intervention, management algorithms have been developed for suspected AEs of selected categories. [see current Investigator Brochure for citation examples]

Dose delay criteria apply for all drug-related adverse events (regardless of whether or not the event is attributed to nivolumab, ipilimumab or both). All study drugs must be delayed until treatment can resume.

Nivolumab and ipilimumab administration should be delayed for the following:

- Any Grade ≥ 2 non-skin, drug-related adverse event, with the following exceptions:
 - Grade 2 drug-related fatigue or laboratory abnormalities do not require a treatment delay
- Any Grade 3 skin, drug-related adverse event
- Any Grade 3 drug-related laboratory abnormality, with the following exceptions for asymptomatic amylase or lipase, AST, ALT, or total bilirubin:
 - Grade 3 amylase or lipase abnormalities that are not associated with symptoms or clinical manifestations of pancreatitis do not require a dose delay. It is recommended to consult with the principle investigator for Grade 3 amylase or lipase abnormalities.
 - If a subject has a baseline AST, ALT, or total bilirubin that is within normal limits, delay dosing for drug-related Grade ≥ 2 toxicity
 - If a subject has baseline AST, ALT, or total bilirubin within the Grade 1 toxicity range, delay dosing for drug-related Grade ≥ 3 toxicity
- Any adverse event, laboratory abnormality, or intercurrent illness which, in the judgment of the investigator, warrants delaying the dose of study medication.

Criteria to Resume Treatment

Subjects may resume treatment with study drug when the drug-related AE(s) resolve to Grade ≤ 1 or baseline value, with the following exceptions:

- Subjects may resume treatment in the presence of Grade 2 fatigue
- Subjects who have not experienced a Grade 3 drug-related skin AE may resume treatment in the presence of Grade 2 skin toxicity
- Subjects with baseline Grade 1 AST/ALT or total bilirubin who require dose delays for reasons other than a 2-grade shift in AST/ALT or total bilirubin may resume treatment in the presence of Grade 2 AST/ALT OR total bilirubin
- Subjects with combined Grade 2 AST/ALT AND total bilirubin values meeting discontinuation parameters should have treatment permanently discontinued

- Drug-related pulmonary toxicity, diarrhea, or colitis, must have resolved to baseline before treatment is resumed
- Drug-related endocrinopathies adequately controlled with only physiologic hormone replacement may resume treatment

If the criteria to resume treatment are met, the subject should restart treatment at the next scheduled timepoint per protocol. However, if the treatment is delayed past the next scheduled timepoint per protocol, the next scheduled timepoint will be delayed until dosing resumes. If treatment is delayed > 6 weeks, the subject must be permanently discontinued from study therapy, except as specified in discontinuation section.

Discontinuation Criteria

Treatment should be permanently discontinued for the following:

- Any Grade 2 drug-related uveitis or eye pain or blurred vision that does not respond to topical therapy and does not improve to Grade 1 severity within the re-treatment period OR requires systemic treatment
- Any Grade 3 non-skin, drug-related adverse event lasting > 7 days, with the following exceptions for drug-related laboratory abnormalities, uveitis, pneumonitis, bronchospasm, diarrhea, colitis, neurologic adverse event, hypersensitivity reactions, and infusion reactions
 - Grade 3 drug-related uveitis, pneumonitis, bronchospasm, colitis, neurologic adverse event, hypersensitivity reaction, or infusion reaction of any duration requires discontinuation
 - Grade 3 drug-related laboratory abnormalities do not require treatment discontinuation except those noted below
 - Grade 3 drug-related thrombocytopenia > 7 days or associated with bleeding requires discontinuation
 - Any drug-related liver function test (LFT) abnormality that meets the following criteria require discontinuation:
 - AST or ALT $> 8 \times$ ULN
 - Total bilirubin $> 5 \times$ ULN
 - Concurrent AST or ALT $> 3 \times$ ULN and total bilirubin $> 2 \times$ ULN
- Any Grade 4 drug-related adverse event or laboratory abnormality, except for the following events which do not require discontinuation:
 - Isolated Grade 4 amylase or lipase abnormalities that are not associated with symptoms or clinical manifestations of pancreatitis and decrease to $<$ Grade 4 within 1 week of onset.

- Isolated Grade 4 electrolyte imbalances/abnormalities that are not associated with clinical sequelae and are corrected with supplementation/appropriate management within 72 hours of their onset
- Any dosing interruption lasting > 6 weeks with the following exceptions:
 - Dosing interruptions to allow for prolonged steroid tapers to manage drug-related adverse events are allowed. Prior to re-initiating treatment in a subject with a dosing interruption lasting > 6 weeks, the Investigator must be consulted. Tumor assessments should continue as per protocol even if dosing is interrupted
 - Dosing interruptions > 6 weeks that occur for non-drug-related reasons may be allowed if approved by the Investigator. Prior to re-initiating treatment in a subject with a dosing interruption lasting > 6 weeks, the Investigator must be consulted. Tumor assessments should continue as per protocol even if dosing is interrupted
 - Any adverse event, laboratory abnormality, or intercurrent illness which, in the judgment of the Investigator, presents a substantial clinical risk to the subject with continued nivolumab or ipilimumab dosing

Treatment of Nivolumab or Ipilimumab Related Infusion Reactions

Since nivolumab and ipilimumab contain only human immunoglobulin protein sequences, it is unlikely to be immunogenic and induce infusion or hypersensitivity reactions. However, if such a reaction were to occur, it might manifest with fever, chills, rigors, headache, rash, pruritis, arthralgias, hypo- or hypertension, bronchospasm, or other symptoms.

All Grade 3 or 4 infusion reactions should be reported as an SAE if criteria are met. Infusion reactions should be graded according to NCI CTCAE 4.0 guidelines.

Treatment recommendations are provided below and may be modified based on local treatment standards and guidelines as appropriate:

For Grade 1 symptoms: (Mild reaction; infusion interruption not indicated; intervention not indicated)

Remain at bedside and monitor subject until recovery from symptoms. The following prophylactic premedications are recommended for future infusions: diphenhydramine 50 mg (or equivalent) and/or paracetamol 325 to 1000 mg (acetaminophen) at least 30 minutes before additional nivolumab administrations.

For Grade 2 symptoms: (Moderate reaction requires therapy or infusion interruption but responds promptly to symptomatic treatment [eg, antihistamines, non-steroidal anti inflammatory drugs, narcotics, corticosteroids, bronchodilators, IV fluids]; prophylactic medications indicated for 24 hours).

Stop the nivolumab or ipilimumab infusion, begin an IV infusion of normal saline, and treat the subject with diphenhydramine 50 mg IV (or equivalent) and/or paracetamol 325 to 1000 mg

(acetaminophen); remain at bedside and monitor subject until resolution of symptoms. Corticosteroid or bronchodilator therapy may also be administered as appropriate. If the infusion is interrupted, then restart the infusion at 50% of the original infusion rate when symptoms resolve; if no further complications ensue after 30 minutes, the rate may be increased to 100% of the original infusion rate. Monitor subject closely. If symptoms recur then no further nivolumab or ipilimumab will be administered at that visit. Administer diphenhydramine 50 mg IV, and remain at bedside and monitor the subject until resolution of symptoms. The amount of study drug infused must be recorded on the electronic case report form (eCRF). The following prophylactic premedications are recommended for future infusions: diphenhydramine 50 mg (or equivalent) and/or paracetamol 325 to 1000 mg (acetaminophen) should be administered at least 30 minutes before additional nivolumab or ipilimumab administrations. If necessary, corticosteroids (recommended dose: up to 25 mg of IV hydrocortisone or equivalent) may be used.

For Grade 3 or Grade 4 symptoms: (Severe reaction, Grade 3: prolonged [ie, not rapidly responsive to symptomatic medication and/or brief interruption of infusion]; recurrence of symptoms following initial improvement; hospitalization indicated for other clinical sequelae [eg, renal impairment, pulmonary infiltrates]). Grade 4: (life threatening; pressor or ventilatory support indicated).

Immediately discontinue infusion of nivolumab or ipilimumab. Begin an IV infusion of normal saline, and treat the subject as follows. Recommend bronchodilators, epinephrine 0.2 to 1 mg of a 1:1,000 solution for subcutaneous administration or 0.1 to 0.25 mg of a 1:10,000 solution injected slowly for IV administration, and/or diphenhydramine 50 mg IV with methylprednisolone 100 mg IV (or equivalent), as needed. Subject should be monitored until the investigator is comfortable that the symptoms will not recur. Nivolumab or ipilimumab will be permanently discontinued. Investigators should follow their institutional guidelines for the treatment of anaphylaxis. Remain at bedside and monitor subject until recovery from symptoms. In the case of late-occurring hypersensitivity symptoms (eg, appearance of a localized or generalized pruritis within 1 week after treatment), symptomatic treatment may be given (eg, oral antihistamine, or corticosteroids).

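### Grade 3 diarrhea is taken out of the 7-day discontinuation rule, but nothing is put in its place

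*Combined protocol and SAP*

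**What the plan says.** All the rules are in section 6 of the protocol.

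- **Base rule (Discontinuation Criteria).** Permanent discontinuation for "Any Grade 3 non-skin, drug-related adverse event lasting > 7 days".
- **Exception list, same bullet.** The rule applies "with the following exceptions for drug-related laboratory abnormalities, uveitis, pneumonitis, bronchospasm, diarrhea, colitis, neurologic adverse event, hypersensitivity reactions, and infusion reactions".
- **Sub-bullet for named events.** "Grade 3 drug-related uveitis, pneumonitis, bronchospasm, colitis, neurologic adverse event, hypersensitivity reaction, or infusion reaction of any duration requires discontinuation".
- **Sub-bullets for laboratory abnormalities.** Grade 3 laboratory abnormalities do not lead to discontinuation, apart from listed thrombocytopenia and liver-test cases.
- **Criteria to Resume Treatment.** "Drug-related pulmonary toxicity, diarrhea, or colitis, must have resolved to baseline before treatment is resumed". If a delay exceeds 6 weeks, "the subject must be permanently discontinued from study therapy, except as specified in discontinuation section".
- **Exception to the 6-week limit.** "Dosing interruptions to allow for prolonged steroid tapers to manage drug-related adverse events are allowed". The Investigator must be consulted before restarting, but no maximum length is stated.
- **Dose changes.** "Dose reductions or dose escalations are not permitted".

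Section 6 also recommends the nivolumab investigator brochure's algorithms for immune-related events, which include a gastrointestinal one. The brochure is not among the documents.

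**The concern.** The exception list and the sub-bullets that carry it out should match, and they do not. Diarrhea is removed from the default rule, and no sub-bullet then says what to do with it. Its clinical neighbor, colitis, must stop at any duration.

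This is a patient-safety stopping rule. Because doses may not be reduced, any re-treatment is at full dose, so whether to stop is the main dosing decision after a severe event. If sites follow the literal text, that decision can turn on whether the event is recorded as diarrhea or as colitis.

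The event is not remote. Section 2.2.3 reports, for the Phase 1 study of the combination in melanoma, drug-related diarrhea of any grade in 41.5% of Cohorts 1-3 and 31.7% of Cohort 8. It lists both diarrhea and colitis among the most frequent serious events and records one death from drug-related enterocolitis. Cohort 8 received nivolumab 1 mg/kg with ipilimumab 3 mg/kg, which section 5.1 prescribes as induction for melanoma, small cell lung, breast and bladder cancer.

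**Working it through.** The protocol gives no figure to reproduce here. The check compares two lists and then asks which other rules still reach Grade 3 diarrhea.

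**Step 1. Match each excepted event type to a replacement rule.**

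| Excepted from the 7-day rule | Replacement rule in the sub-bullets |
|---|---|
| Laboratory abnormalities | Own sub-bullets |
| Uveitis | Stop at any duration |
| Pneumonitis | Stop at any duration |
| Bronchospasm | Stop at any duration |
| Diarrhea | **None** |
| Colitis | Stop at any duration |
| Neurologic adverse event | Stop at any duration |
| Hypersensitivity reaction | Stop at any duration |
| Infusion reaction | Stop at any duration |

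Excepted: 9. Covered: 7 (any duration) + 1 (laboratory) = 8. Remainder: 9 − 8 = 1, which is diarrhea.

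**Step 2. List the general rules that still apply to Grade 3 drug-related diarrhea.**

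- Dosing is delayed, as for any non-skin drug-related event of Grade 2 or higher. This is a delay, not a stop.
- Diarrhea must return to baseline before dosing resumes. This sets when to restart, not whether to.
- A delay beyond 6 weeks (6 × 7 = 42 days) requires discontinuation, except for prolonged steroid tapers.
- Grade 4 events are covered, but that is a different grade.
- Investigator-judged risk (section 6) and unacceptable adverse events (section 5.5) can end treatment. Both depend on judgment.

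None of these says whether Grade 3 diarrhea stops treatment at any duration, after 7 days, or not at all.

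**Step 3. Test whether the 6-week limit stands in for the 7-day rule.** It does not, because it counts dosing delay and the 7-day rule counts event duration. As an illustration on the every-3-weeks schedule, take a dose on day 1, with the next due on day 1 + 21 = 22. Suppose Grade 3 diarrhea runs from day 4 to day 14 and is back to baseline by day 21.

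- Event duration: 14 − 4 = 10 days, which is more than 7. The base rule would stop this patient.
- Dosing delay: 0 days. The 42-day limit is never engaged, and on the literal reading the patient is re-dosed on day 22.
- The same course recorded as Grade 3 colitis: permanent discontinuation.

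**Step 4. Ask whether the omission looks deliberate.** Where section 6 means to exempt a class from stopping, it says so, as it does for laboratory abnormalities. There is no such statement for diarrhea. The return-to-baseline rule does not serve as one either: it also names pulmonary toxicity and colitis, yet Grade 3 pneumonitis and colitis still stop at any duration.

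**The case against.** The strongest reply is that the exceptions are whatever the sub-bullets state. Since no sub-bullet exempts diarrhea, the 7-day rule still governs it and no protection is lost. That reading is available and cannot be excluded. But it makes the word diarrhea in the exception list meaningless, so the text still needs correcting.

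A second reply is that diarrhea was excepted on purpose and is managed by delay until it returns to baseline, which is tighter than the usual Grade 1 threshold for restarting. Step 4 makes this unlikely, though the documents do not rule it out.

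Third, the brochure's gastrointestinal algorithm may supply the missing instruction. That cannot be checked here. The protocol cites the algorithms as a recommendation, and they would not reconcile the protocol's own two lists.

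Three further points stand and limit the claim:

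- Seven days of event and 42 days of delay are different clocks, so the change is not a measured relaxation from one to the other.
- The open-ended steroid-taper exception applies to every drug-related event, not to diarrhea alone.
- Deleting diarrhea from the exception list would still leave shorter Grade 3 diarrhea and colitis under different rules. Different rules for two separately named events are not in themselves an error.

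**Conclusion.** The concern holds. Nine event types are excepted from the 7-day rule, eight have a replacement, and diarrhea has none. On the literal reading, Grade 3 diarrhea loses its limit on event duration. What remains fixed is a 42-day limit on dosing delay, with no stated maximum when the delay is for a steroid taper. On the alternative reading the 7-day rule survives and one word in the exception list is wrong. The protocol does not choose between them.

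The list count is certain. The consequence for patients depends on the literal reading and on the unseen brochure not settling the matter in practice. The documents give no Grade 3 diarrhea rate, so the number of patients affected cannot be estimated. No endpoint, sample size or analysis changes. The sponsor should correct this because it is an ambiguous safety stopping rule in a trial where re-treatment is always at full dose.

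**What to change.** In section 6, Discontinuation Criteria, make one of two edits:

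- **(a)** Delete diarrhea from the exception list, so that Grade 3 diarrhea lasting more than 7 days leads to discontinuation.
- **(b)** Add diarrhea beside colitis in the any-duration sub-bullet. This is stricter, and it also removes the dependence on which of the two terms is recorded.

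The sponsor's clinicians should choose, and should check the choice against the brochure's gastrointestinal algorithm. At a minimum the 7-day limit should apply without ambiguity. The cost is one word in the protocol.

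### Section 6 gives an infusion reaction that recurs after restart a visit-limited stop under Grade 2, but its own Grade 3 wording makes the same event a permanent stop

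*Combined protocol and SAP*

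**What the plan says.** All the relevant text is in section 6 of the protocol, under the Discontinuation Criteria and the infusion-reaction guidance that follows them.

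- **Grade 2, definition:** "Moderate reaction requires therapy or infusion interruption but responds promptly to symptomatic treatment".
- **Grade 2, restart:** after an interruption, staff "restart the infusion at 50% of the original infusion rate when symptoms resolve".
- **Grade 2, recurrence:** "If symptoms recur then no further nivolumab or ipilimumab will be administered at that visit". The paragraph then gives a treatment for the recurrence (intravenous diphenhydramine and bedside observation).
- **Grade 2, later visits:** "The following prophylactic premedications are recommended for future infusions"; these "should be administered at least 30 minutes before additional nivolumab or ipilimumab administrations".
- **Grade 3, descriptor:** the list includes "recurrence of symptoms following initial improvement; hospitalization indicated for other clinical sequelae".
- **Grade 3/4, action:** "Nivolumab or ipilimumab will be permanently discontinued".
- **Discontinuation Criteria:** a Grade 3 drug-related "hypersensitivity reaction, or infusion reaction of any duration requires discontinuation".

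Two framing statements introduce the infusion-reaction guidance. Reactions are to be graded by CTCAE 4.0, and the treatment advice is a set of recommendations that sites may adapt to local standards. The Discontinuation Criteria carry no such allowance for Grade 3 infusion reactions.

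**The concern.** Two neighbouring paragraphs cover the same bedside event and lead to different places. Read alone, the Grade 2 paragraph withholds drug for the day and then turns to premedication for later infusions. Read alone, the Grade 3/4 paragraph ends treatment for good. Nothing says which one governs once a restarted infusion has to be stopped again.

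The first thing at stake is patient safety, since the question is whether a patient is exposed again to a drug that has just caused a recurrent reaction. Several records also depend on the answer:

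- the severity grade in the adverse-event tables (section 13.6);
- the SAE assessment, because section 6 singles out Grade 3 and 4 infusion reactions for SAE reporting where criteria are met;
- the reason and date of removal from protocol therapy (section 5.5);
- the dates counted from the end of dosing: the first follow-up visit (section 5.6) and the 100-day SAE window (section 7.10).

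**Working it through.** The plan states no figure on this point and no arithmetic applies. The check follows one patient through the three pieces of text.

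1. A reaction needs an interruption and responds promptly to treatment. By the printed definition it is Grade 2.
2. The infusion is restarted at half rate. The restart is conditional on the symptoms having resolved.
3. Symptoms come back. Step 2 required resolution, so this is necessarily a return of symptoms after improvement.
4. The printed Grade 3 descriptor lists recurrence after improvement between semicolons, as an item separate from a prolonged reaction and from hospitalization. The event in step 3 meets it, and it does so in every case.

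The instructions for that single event are then:

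| Source in section 6 | Extent of stop | Later treatment |
|---|---|---|
| Grade 2 paragraph | That visit | Premedication recommended before further infusions, with no exception for recurrence |
| Grade 3/4 paragraph | Permanent | None for the drug or drugs concerned |
| Discontinuation Criteria | Permanent, whatever the duration | None |

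5. I looked for a sentence that links the rows. None says that recurrence after restart is to be re-graded, and none gives an order of precedence.

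6. The two permanent-stop texts also differ in scope. The Grade 3/4 action names nivolumab or ipilimumab, while the Discontinuation Criteria speak of treatment as a whole. The dose-delay rule in the same section holds all study drugs whichever one is blamed, but it governs delays and not permanent stops.

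**The case against.** The best defence is that the text works if staff grade first and act second. Reactions are graded by CTCAE 4.0, Grade 2 is reserved for reactions that respond promptly, and recurrence is listed under Grade 3. A recurrent reaction would then become Grade 3, and the Discontinuation Criteria would end treatment. The Grade 2 recurrence sentence would only be the immediate step of not attempting another restart, which is compatible with a later permanent stop.

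That reading is possible, but the protocol never states it. It also leaves two things hard to explain: why the stop is limited to one visit, and why recurrence has its own treatment inside the Grade 2 paragraph, different from the Grade 3/4 treatment.

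Parts of the defence do stand, and they rule out some stronger inferences.

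- **That the protocol orders the same patient to be both re-treated and stopped.** It does not. Re-treatment after a recurrence is implied by the visit-limited stop and the premedication advice. That advice also serves the ordinary Grade 2 case in which the restart succeeds.
- **That either course is fully compliant.** The infusion-reaction paragraphs may be adapted locally and the Discontinuation Criteria may not. Re-treating a patient whose event meets the printed Grade 3 wording would conflict with those criteria.
- **That a case is likely in this trial.** The documents give no rate and call infusion reactions unlikely. With 20 patients, the chance of at least one case is 1 − (1 − p)^20. Assumed values of p of 0.1%, 1% and 5% give about 2%, 18% and 64%. A range that wide says nothing beyond the assumption.
- **That the main results are at risk.** Survival runs from registration to death (section 11.1.6), and the endpoint is survival at 3 months (section 13.1). The named toxicity endpoint counts hematologic and neurologic events of Grade 3 or higher, and does not name infusion reactions. A permanent stop at the first dose could raise a question under the one-cycle requirement of section 13.8.2, but so would any early stop. It changes neither the endpoint definition nor the Simon thresholds.

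**Conclusion.** The conflict is real and narrow. A recurrence after restart always falls within the printed Grade 3 descriptor, while the Grade 2 paragraph manages it with a stop for that visit and wording that implies later infusions. The protocol does not say which governs. Whether the permanent stop covers one drug or both is a second, smaller ambiguity in the same text.

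The size cannot be expressed as a rate. The event is expected to be rare, and the effect is on safety handling, the recorded grade, the SAE assessment and the off-treatment record. A higher grade alone does not make the event an SAE, because the protocol ties reporting to the criteria being met.

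The conclusion rests on two readings: that the Grade 3 descriptors are alternatives, as their punctuation suggests, and that premedication for later infusions carries its ordinary meaning when it follows the recurrence instruction without an exception. It is worth correcting because it concerns a stopping rule and the correction is cheap.

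**What to change.** Reconcile the Grade 2 paragraph, the Grade 3/4 paragraph and the Discontinuation Criteria in section 6 so that a reaction recurring after restart has one stated grade and one stated consequence. Remove or cross-refer the text that then disagrees. In the same edit, make the Grade 3/4 action and the Discontinuation Criteria agree on whether one drug or both stop. Which rule holds is for the sponsor and investigator to decide.

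The cost is a wording amendment to section 6, with no added procedures or patients and no change to the statistical design.
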